After surgery, the patient will be given a standardized voiding trial as per the usual protocol. If the patient is un-successful in emptying her bladder according to the VT protocol she will be discharged home with an indwelling Foley catheter as per usual protocol. On post-operative day (POD) #1 the patient will be re-assessed for meeting eligibility requirements. Once eligibility is established, the subject will be called on POD#1 and randomized to either the early voiding trial group (EVT) or the late voiding trial group (LVT). Subjects in EVT will be scheduled for a repeat VT on POD#2-4, whereas those in LVT will be scheduled for a repeat VT on or after POD#7. Subjects that are unsuccessful in the repeat VT will have a Foley catheter re-inserted and will return for another VT in 5-7 days. Subjects who fail the third VT from either group will have the Foley catheter replaced and will return for another office VT after waiting an additional 5-7 days or will be started on clean intermittent self-catheterization.

Subjects will be monitored for a 6 week period. During that time the patient will be monitored for voiding and urinary symptoms. Urine will be tested via in-office urinalysis at each office visit (as per usual practice), including pre-operatively, and will be sent for a urine culture per usual practice based upon abnormal urinalysis results (ie. any blood or leukocytes). Urine cultures that grow out a single organism >10,000 CFU will be treated with appropriate antibiotics. In addition, patients will complete quality of life questionnaires at the time of catheter removal and at 6weeks post-operatively.

Setting

The study will take place at two medical centers. Most of the interactions will take place in the office setting, including all pre-operative evaluations, and post-operative follow-up. Surgeries will be performed in the hospital setting.

Subjects selection criteria

Inclusion Criteria

Subjects must meet the following inclusion criteria in order to be eligible for the study

- Female patients age 18 or older
- Speak English and are capable of giving informed consent
- Are willing to return to the office for all necessary visits associated with the study
- Underwent outpatient gynecology pelvic floor surgery for multi-compartment prolapse
- Failed the voiding trial in the recovery room on POD#0

Exclusion Criteria

Subjects must not have any of the following exclusion criteria in order to be eligible for the study

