- Pre-operative urinary retention as defined as PVR > 200ml
- Prior incontinence surgery
- Passed the voiding trial in the recovery room

- Require prolonged catheterization due to urethral/bladder abnormality (ie vesicovaginal fistula, urethral diverticulum) or intra-op urethral or bladder injury or for intensive post-operative monitoring
- Patients who take any post-operative antibiotics, other than prophylaxis during catheterization, for reasons other than a UTI as diagnosed and prescribed as part of the study
- Patients who take any supplements to prevent UTIs, including but not limited to D-Mannose, Hiprex, or Ellura
- Have any neurological conditions that may affect bladder function (ie. Multiple sclerosis, spinal cord injuries, etc.)
- Patients with pre-operative narcotic medication use due to chronic pain

• Sample Size

Using OpenEpi.com and the Fleiss statistical method the sample size was calculated for a randomized controlled trial based on the Hakvoort et al. study. With a 95% two-sided significance and an 80% power, this study will need 60 subjects to be adequately powered to test for the primary outcome of differences in Foley catheter re-insertion rates.

• This is a multi-center study. The coordinating institution is the Cleveland Clinic Florida in Weston, FL. The study has been approved and enrollment is underway at that site. Over 30 patients are already enrolled at that site. Ideally, 20 subjects would be enrolled from Wake Forest Baptist Health in North Carolina.

Interventions and Interactions

- As described above, if the patient does not pass the recovery room VT, a Foley catheter will be inserted for either 2-4 or 7 days depending on the randomization. Prophylactic antibiotics may be used per the surgeon's preference. Length of catheter duration will depend on when the patient is able to pass an outpatient VT.
- As described above, urine cultures will be performed as medically indicated. A single identified organism of 10,000 CFU or greater will be considered a positive culture.
- Pre-operative and post-operative questionnaires will be used to assess patient satisfaction with their voiding/ Foley catheter use.
- Office notes will be reviewed to assess for study eligibility. Background data will be
 collected for descriptive statistics. Data from urodynamic studies will also be collected as part
 of the background data. Post-operative notes from the clinic will be reviewed to assess for

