 any complications or adverse events. Surgical and hospital records will be reviewed and
 various data will be collected to ensure that there was equivalence in the groups for items
 such as: type of surgery, post-op narcotic use, length of surgery, time to recovery room void
 trial, etc.

Length of time spent by each subject on specific study materials will only include the length of time to complete the short questionnaires. The remainder of their care, including surgery, post-operative follow-up, repeat VT are part of the usual post-operative care

			Visit			
	Pre-Study	Recovery Room	V#1 (Repeat VT, either POD 2-4 or 6-7)	V#2 (Repeat VT if failed at V#1 Or 2 week post- op visit)	V#3 (2 week routine post-op visit or 6 week post- op visit)	V#4 (6 week post-op visit, if not completed at V#3)
Informed Consent	X					

Demographics	X					
Medical History	X		X	X	X	X
Physical Exam	X			X	X	X
Pre-operative Labs	X					
Urodynamic	X					
Testing	Λ					
Voiding Trial		X	X	X		
Patient	v		X	v	v	v
Questionnaire	Λ		Λ	Λ	Λ	Λ
Urine Sample	X		X	X	X	X

Outcome Measure(s)

• Outcomes that will be assessed include: void trial outcomes, UTI rates, urinary retention rates, and patient satisfaction.

Human Subjects Protection

Subject Recruitment Methods

Upcoming surgical schedules will be reviewed 1-2 weeks prior to surgery. Patients will be contacted by a member of the study team to discuss eligibility, review the inclusion/exclusion criteria, and to answer all questions. Consent will be signed prior to surgery. Any subject who wishes to withdraw from the study may do so at any time. When the subject chooses to withdraw, they will be presented with the option to either allow all of the data collected to that point be retained, or if they would like it to be removed.

All data will be kept on secure password protected and encrypted hospital computers and contained within password protected files. Source documents will be kept in a locked drawer on hospital property. Protected health information will be de-identified.

Informed Consent

Signed informed consent will be obtained from each subject. Consent will be obtained by one of the study staff prior to surgery.

Confidentiality and Privacy

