Title: Optimal timing of a second post-operative voiding trial in women with incomplete bladder emptying after vaginal reconstructive surgery: a randomized trial

NCT: NCT03048682 **DATE**: December 15, 2018

Statistical Analysis Plan

Descriptive statistics were calculated for the overall sample. The data was assessed using an intention-to-treat analysis. Continuous data with normal distribution were analyzed using Student's t-test, whereas skewed data were analyzed using a Wilcoxon signed-rank test. Categorical data, such as void trial failure rates (the primary outcome), were analyzed using Pearson's chi-square test or Fisher's exact test if there were ≤5 subjects in 20 % of the cells. Patients bother as noted on a Likert scale was considered as ordinal data. Univariate analysis as well as a forward stepwise multivariate regression analysis were performed. A p-value of less than 0.05 was considered statistically significant. All analyses were performed using JMP version 14.0.0 (SAS Institute Inc., Cary, NC).

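### The SAP commits to no use of the pre-operative satisfaction score; pre-specified adjustment for it at 6 weeks would add power to a secondary comparison at almost no cost

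*Protocol*

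**What the plan says.** The protocol lists patient satisfaction among its Secondary Objectives and again under Outcome Measure(s).

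It describes the questionnaires in three places:

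- Design: "patients will complete quality of life questionnaires at the time of catheter removal and at 6weeks post-operatively".
- Interventions and Interactions: "Pre-operative and post-operative questionnaires will be used to assess patient satisfaction", where the satisfaction in question covers both voiding and use of the Foley.
- Visit table: the questionnaire row is marked at Pre-Study and at V#1 to V#4. Some marks are garbled in the extracted text but read as crosses.

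These are compatible. Design lists post-operative occasions, and the other two places add the pre-operative one. Women are randomised by telephone on post-operative day 1, so the pre-operative score is fixed before allocation.

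On analysis, the SAP says "Patients bother as noted on a Likert scale was considered as ordinal data". It also reports univariate analysis and a forward stepwise multivariate regression, but gives neither the outcome nor the candidate variables of that regression. It names no time point, between-arm ordinal method or covariate for satisfaction or bother.

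**The concern.** A score measured before randomisation on the same item as the outcome is usually one of the strongest predictors of that outcome. Using it costs nothing when it is already collected. The trial plans about 30 women per group, a number set for the primary outcome and not for satisfaction, so power for satisfaction is limited and worth protecting.

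As written, the SAP leaves the pre-operative score either unused or dependent on forward selection. Selection is not pre-specified adjustment: whether the covariate enters depends on the data, and so does the model from which the arm effect is read. What is at stake is power and clarity on one secondary comparison.

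**Working it through.** **The plan's own figure.** There is none to reproduce for satisfaction. The 60 subjects (30 per group, two-sided 5% level, 80% power) refer to the primary outcome. I use 30 per group only as the number available.

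**Inputs.** n = 30 per group, two-sided alpha 0.05 and power 80% come from the protocol (Design; Sample Size). The correlation r between the pre-operative and 6-week scores is not in the documents, so a range is assumed. Scores are treated as continuous, in standard deviation (SD) units.

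**Unadjusted comparison.** Detectable difference = (1.960 + 0.842) × √(2/30) = 2.802 × 0.258 = 0.72 SD at 80% power.

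**Adjusted comparison (linear model).** Residual variance is multiplied by 1 − r². The detectable difference is multiplied by √(1 − r²). Power at 0.72 SD is Φ(2.802/√(1 − r²) − 1.960). The equivalent unadjusted number per group is 30/(1 − r²), rounded up.

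| r (assumed) | 1 − r² | Variance reduction | Detectable difference | Power at 0.72 SD | Equivalent n per group |
|---|---|---|---|---|---|
| 0 | 1.00 | 0% | 0.72 SD | 80.0% | 30 |
| 0.3 | 0.91 | 9% | 0.69 SD | 83.6% | 33 |
| 0.4 | 0.84 | 16% | 0.66 SD | 86.4% | 36 |
| 0.5 | 0.75 | 25% | 0.63 SD | 89.9% | 40 |

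**Limit of this table.** The factor 1 − r² belongs to linear models. Under proportional odds, adjustment changes the target to a conditional odds ratio. The gain appears as power to detect that ratio, not as a smaller standard error. The table therefore shows the likely order of the gain and is not a derivation for the recommended model.

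**Which occasions are comparable across arms.** The 6-week visit falls at the same post-operative age in both arms by design. Catheter removal does not:

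- The early arm's repeat voiding trial is on day 2 to 4.
- Design places the late arm's trial on or after day 7, with no upper limit. The visit table has V#1 at "either POD 2-4 or 6-7".
- The scheduled gap is thus 7 − 4 = 3 to 7 − 2 = 5 days using day 7, or 6 − 4 = 2 to 7 − 2 = 5 days using the table.
- After a failure, "Subjects that are unsuccessful in the repeat VT will have a Foley catheter re-inserted and will return for another VT in 5-7 days". An early-arm woman who fails returns between day 2 + 5 = 7 and day 4 + 7 = 11, which overlaps the late arm. Removal day therefore also depends on the voiding-trial result.

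**The case against.** **A stronger reading that does not hold.** A reader might infer that satisfaction is compared at catheter removal without the baseline, so that arm is confounded with recovery time. The documents do not support this. The SAP names no time point and does not exclude the baseline, and the protocol also schedules 6 weeks. Nor is confounding the right word: removal day follows from randomised allocation, so scores at removal are a valid contrast of the two strategies as experienced. They simply cannot separate catheter duration from days since surgery, and no stated objective asks for that separation.

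**The stepwise regression may already include the baseline.** It may, but neither its outcome nor its candidates are named, and forward selection commits to nothing.

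**There may be no usable baseline.** This stands in part. The questionnaire items cannot be seen in the text available, and women have no study catheter before surgery, so Foley-specific items have no pre-operative counterpart. If the SAP's bother means catheter bother, adjustment does not apply to it. The stated construct also covers voiding, where a matching item is plausible, so the point is confined to matching items.

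**Six weeks is late for judging the Foley experience.** This is fair, and it is why removal scores should still be reported. The 6-week comparison proposed here concerns voiding items.

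**The size is assumed.** This stands. The correlation has no source in the documents, and the gain is nil at r = 0.

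**Conclusion.** The point holds as a small, nearly free improvement. The protocol collects a pre-operative satisfaction score and the SAP does not commit to using it. For voiding-satisfaction items asked both before and after surgery, pre-specified adjustment should add power: on the linear approximation, from nothing at r = 0 to a 25% cut in residual variance at r = 0.5.

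This assumes that matching items exist, that the pre/post correlation is above zero, and that the linear figures are a fair guide to an ordinal model. Only a secondary outcome is affected. The documents give no ground for calling the planned comparison biased.

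**What to change.** In the SAP:

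1. For each voiding-satisfaction item asked both before and after surgery, compare arms at 6 weeks with a proportional-odds model containing arm and the pre-operative score. Fix that covariate in advance, outside the stepwise procedure, and report the result as a conditional odds ratio with its confidence interval.
2. Leave Foley-specific items unadjusted.
3. Report catheter-removal scores separately as a contrast of the strategies as experienced, noting that they cannot separate catheter duration from days since surgery.
4. State how a missing pre-operative score will be handled.

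In the protocol, reconcile the late-arm timing between Design (on or after day 7) and the visit table (day 6 to 7). The table already schedules the pre-operative questionnaire, so no new data collection is needed.

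The cost is a few sentences and one ordinal model. The SAP is written in the past tense. If analysis had already begun, the adjusted model should be labelled post hoc and shown beside the unadjusted result.

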Appendix

Title: Optimal timing of a second post-operative voiding trial in women with incomplete bladder emptying after vaginal reconstructive surgery: a randomized trial

NCT: NCT03048682 **DATE**: December 15, 2018

Statistical Analysis Plan

Descriptive statistics were calculated for the overall sample. The data was assessed using an intention-to-treat analysis. Continuous data with normal distribution were analyzed using Student's t-test, whereas skewed data were analyzed using a Wilcoxon signed-rank test. Categorical data, such as void trial failure rates (the primary outcome), were analyzed using Pearson's chi-square test or Fisher's exact test if there were ≤5 subjects in 20 % of the cells. Patients bother as noted on a Likert scale was considered as ordinal data. Univariate analysis as well as a forward stepwise multivariate regression analysis were performed. A p-value of less than 0.05 was considered statistically significant. All analyses were performed using JMP version 14.0.0 (SAS Institute Inc., Cary, NC).

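### The SAP names a paired test, the Wilcoxon signed-rank, for skewed data although the two arms are independent; non-primary comparisons only

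*SAP*

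**What the plan says.** The SAP gives one rule for continuous variables. The first half reads "Continuous data with normal distribution were analyzed using Student's t-test"; the second half reads "whereas skewed data were analyzed using a Wilcoxon signed-rank test". Nothing limits the second half to changes within a patient, and no rank-sum or Mann-Whitney test appears in either document.

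The protocol (Methods and Measures, Design) has each eligible woman called on the first post-operative day and "randomized to either the early voiding trial group (EVT) or the late voiding trial group (LVT". These are two parallel groups of different women; no matching or crossover is described.

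Under Interventions and Interactions, the protocol collects surgical and hospital data to check that the groups are comparable, including "type of surgery, post-op narcotic use, length of surgery, time to recovery room void" trial. The same section says "Pre-operative and post-operative questionnaires will be used to assess patient satisfaction" with voiding and catheter use.

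For other data types the SAP says "Categorical data, such as void trial failure rates (the primary outcome), were analyzed using Pearson's chi-square test or Fisher's exact test" (the latter when cell counts are small), and "Patients bother as noted on a Likert scale was considered as ordinal data". No test is attached to that ordinal scale. The significance rule is "A p-value of less than 0.05 was considered statistically significant".

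**The concern.** Signed-rank ranks the absolute differences within pairs. It applies to one sample of differences, such as a patient's score before and after surgery. Early and late arms contain different women, so there are no natural pairs and no differences to rank.

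Taken literally, the SAP therefore prescribes a test that either cannot be run or requires the analyst to invent a pairing that the document does not define. Two analysts following the text could then report different p-values from the same data. Because the SAP reports what was done rather than what will be done, a reader cannot tell whether signed-rank was actually used between arms or whether the name is wrong.

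**Working it through.** The plan states no figure on this point, so there is none to reproduce. The check is one of fit between test and design, followed by an illustration of size.

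**Step 1: test against design**

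| Item | What the documents give | Does signed-rank fit? |
|---|---|---|
| Repeat voiding-trial failure (primary) | Categorical; chi-square or Fisher | Not used |
| UTI, catheter re-insertion | Rates, so categorical | Not used |
| Length of surgery, time to recovery-room voiding trial, narcotic use (if recorded as an amount) | Between-arm balance; signed-rank if skewed | No: independent groups |
| Likert bother | Ordinal; no test named | Not stated |
| Change in questionnaire scores within a patient | Repeated questionnaires exist; no paired analysis specified | It would fit, but is not planned |

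The only use that the SAP's wording reaches is the one in which the test does not fit.

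**Step 2: what each test needs**

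- Signed-rank: form d_i = x_i − y_i for n pairs, rank |d_i|, and sum the ranks of the positive d_i. Under the null the sum has mean n(n+1)/4 and variance n(n+1)(2n+1)/24. Both arms must have the same n, and the value depends on which x is matched to which y.
- Rank-sum: U counts, over all n1 × n2 cross-arm pairs, how often one arm's value exceeds the other's. Under the null it has mean n1·n2/2 and variance n1·n2(n1+n2+1)/12. The arms may differ in size, and no matching is involved.

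With 30 per arm, signed-rank uses 30 differences, while rank-sum uses 30 × 30 = 900 comparisons.

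**Step 3: can it be computed?**

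The protocol plans 60 women, 30 per group, and 66 with 10% drop-out (60 × 1.10 = 66). It gives no allocation method. If simple 1:1 randomisation is assumed, P(exactly equal arms) = C(N, N/2) / 2^N:

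- N = 60: 0.103
- N = 66: 0.098

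So under that assumption the arms would differ in size about 90% of the time. Blocked allocation would make equality likelier, but drop-out or missing values could still break it. In a trial run with 29 against 30 values, the signed-rank routine returned an error.

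**Step 4: if the arms are equal**

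Assumptions, none from the documents: lognormal data, log-SD 1, arbitrary pairing. Settings: 30 per arm, two-sided 0.05, normal approximations, 20,000 simulated trials per row.

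| Log shift between arms | Rejects: signed-rank | Rejects: rank-sum | Two arbitrary pairings disagree |
|---|---|---|---|
| 0 (no effect) | 5.0% | 4.6% | 3.9% |
| 0.5 | 40.7% | 45.0% | 13.5% |
| 0.75 | 73.5% | 79.1% | 11.4% |

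Power loss: 45.0 − 40.7 = 4.3 points and 79.1 − 73.5 = 5.6 points. Type I error holds because, with no effect, the difference between two unrelated values is symmetric about zero, provided the pairing is chosen without looking at the data. Repeat runs with the same settings agreed within simulation error.

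On one fixed simulated dataset (30 per arm, log shift 0.7), 5,000 arbitrary pairings gave signed-rank p-values from 0.000009 to 0.047, against a single rank-sum p of 0.0056.

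**The case against.** The strongest reply has four parts.

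- **Little depends on it.** The variables most clearly reached are balance checks. A few points of power on length of surgery change no conclusion about early versus late voiding trials, and even these variables are reached only if skewed. This stands, and it is why the point is modest.
- **It is probably a naming slip.** If the arms are usually unequal, the test could not have been run between them, so rank-sum was probably meant and nothing numerical is wrong. This is plausible, but the documents do not show it. A past-tense statement of method that names the wrong test still needs correcting.
- **The simulation is hypothetical.** It needs equal arms and an analyst willing to pair unrelated women, and it uses one distribution with one log-SD. In the single-dataset example every pairing stayed below 0.05, so no verdict changed there. This also stands: the percentages illustrate the size and do not estimate what happened in this trial. The mismatch between test and design does not depend on them.
- **A paired use may be intended.** Questionnaires are repeated within patients, and the SAP sentence never says between groups. But no within-patient analysis is specified, the sentence sets signed-rank beside Student's t-test as the general rule for continuous data, and Likert bother is treated separately. If the paired reading were right, skewed between-arm data would have no named test at all.

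**Conclusion.** The point holds. As written, the SAP assigns a paired or one-sample test to skewed data from two independent groups, and this reading rests on the text alone. It should be fixed, but the consequence is limited: the primary outcome, the other categorical outcomes and the sample size are untouched, and false positives are not inflated. What is lost is reproducibility and, if signed-rank was really run on arbitrary pairs, about 4 to 6 points of power, with opposite verdicts between pairings in about 4% to 14% of cases. Those sizes assume lognormal data with log-SD 1, 30 per arm, and log shifts of 0.5 and 0.75 (zero shift for the 4%). The figure of about 10% for equal arms assumes simple randomisation.

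**What to change.** - In the SAP, name the Wilcoxon rank-sum (Mann-Whitney) test for early-versus-late comparisons of skewed continuous data.
- Keep signed-rank only for within-patient change in questionnaire scores, if that is reported, and say so.
- State which procedure was run in JMP. If signed-rank was used between arms, re-run those comparisons with rank-sum.
- As a separate small gap, name a test for the ordinal bother scores; rank-sum is one acceptable choice.

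The cost is one or two sentences of SAP text and, at most, a short re-analysis of existing data. No extra patients or data collection are needed.

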The primary objective of this study is to determine the timing to return to normal bladder function after pelvic floor reconstructive surgery for those patients who failed the initial post-operative VT. To assess this, the rate of failure of repeat VT will be assessed at two post-operative time points.

Secondary Objectives

To evaluate:

- The rates of UTI in the two groups
- Rates of Foley catheter re-insertion after passing a subsequent office void trial
- Patient Satisfaction

Methods and Measures

Design

This study is a randomized controlled trial designed to assess the timing of return to normal bladder function after pelvic floor reconstructive surgery. The primary outcome will be assessed by comparing office VT failure rates between those who return in the early post-operative period (2-4 days) vs the standard time to return for an office VT (1 week). Based on the Hakvoort et al

study and a 95 two-sided significance level and 80% power, this study would require 60 subjects, or 30 per group. Assuming a 10% drop-out rate, 66 total subjects should be enrolled in the study. All patients that meet the appropriate inclusion criteria will be considered for the study. OR schedules will be reviewed and subjects will be assessed for possible eligibility approximately 1-2 weeks prior to surgery. Patients will be counseled about the study either in the office during a surgical planning office visit, over a pre-operative telephone call, or in the pre-operative area just prior to surgery. Consents will be signed in the pre-operative area.

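### The SAP's univariate and forward stepwise regression has no stated outcome, candidate list, entry rule or exploratory label, so if several variables are screened the p-values of those selected do not hold at 0.05 (minor)

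*SAP*

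**What the plan says.** The SAP is a single paragraph. It assigns the primary outcome, "such as void trial failure rates (the primary outcome", to a Pearson chi-square or Fisher's exact test under intention to treat. After a sentence on the Likert bother item it adds: "Univariate analysis as well as a forward stepwise multivariate regression analysis were performed". The next sentence reads: "A p-value of less than 0.05 was considered statistically significant". Nothing limits that rule to the primary test.

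The protocol does not mention regression, and none of its primary or secondary objectives is a search for predictors. Under Outcome Measure(s) it lists "void trial outcomes, UTI rates, urinary retention rates, and patient satisfaction", so the regression could refer to more than one outcome.

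The nearest thing to a covariate list is under Interventions and Interactions: "type of surgery, post-op narcotic use, length of surgery, time to recovery room void" (trial), followed by 'etc.'. These items are collected to check that the groups are equivalent. They are not named as regression candidates. The same section says "Data from urodynamic studies will also be collected as part" of the background data. The planned size, under Design, is given as "this study would require 60 subjects, or 30 per group".

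**The concern.** A forward stepwise procedure tests each candidate, keeps the best if it passes the entry rule, and repeats. The p-value printed beside a retained variable is calculated as if that variable had been the only one considered. With several candidates and a small sample, a retained variable may be a chance finding, and its estimated effect tends to be too large because only large estimates pass.

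The missing details are the ones a reader would need to judge this: which outcome, how many candidates, what entry rule, and whether the result is meant as a hypothesis or a claim. As written, a variable reaching p < 0.05 in this search would be called significant on the same terms as the primary comparison. What is at stake is a report that names a risk factor for failing the repeat voiding trial on evidence much weaker than its p-value suggests.

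**Working it through.** **Inputs from the documents.** n = 60, 30 per arm (Protocol, Design). One threshold of 0.05 with no correction (SAP). Four named background variables plus an open-ended 'etc.' (Protocol, Interventions and Interactions). The plan gives no figure for the regression, so there is none to reproduce.

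**Assumptions, because the documents are silent.** Candidate counts above 4; a logistic model for repeat voiding trial failure; entry at p < 0.05; failure rates of 10%, 20% and 30%, which give 60 × 0.10 = 6, 60 × 0.20 = 12 and 60 × 0.30 = 18 failures.

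**Step 1. Multiplicity, for any outcome or model.** With K independent null tests at 0.05, P(at least one false positive) = 1 − 0.95^K, and the expected number of false positives is 0.05 × K.

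| K | 0.95^K | At least one false positive | Expected number |
|---|---|---|---|
| 4 | 0.815 | 18.5% | 0.20 |
| 5 | 0.774 | 22.6% | 0.25 |
| 10 | 0.599 | 40.1% | 0.50 |
| 15 | 0.463 | 53.7% | 0.75 |

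**Step 2. How much comes from the stepwise procedure itself.** Simulated trials: 30 per arm, 20% failure in both arms, the arm plus K independent standard-normal null candidates, likelihood-ratio entry at 0.05, 1000 replicates per cell. Share of trials with at least one null variable selected:

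| K | Stepwise | Univariate screen |
|---|---|---|
| 4 | 20.6% | 20.4% |
| 5 | 23.5% | 23.6% |
| 10 | 44.7% | 44.7% |
| 15 | 57.3% | 57.1% |

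The columns are almost the same, so at this entry level the false-positive problem is ordinary multiplicity. With candidates correlated at 0.3, the stepwise figures are 19.5%, 24.3%, 39.2% and 49.1%. A separate simulation with the arm forced in and failure rates of 10-30% gave 18-19% at K = 4 and 43-47% at K = 10. Another, with half the candidates binary, gave 25-30% at K = 5 and 44-49% at K = 10.

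**Step 3. Looser entry.** If entry were at p < 0.10 (20% failure in both arms), a null variable would be in the final model in 36.4% of trials at K = 4 and 69.9% at K = 10.

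**Step 4. Size of the selected odds ratios, if the model is logistic.** In the Step 2 setting the true odds ratio is 1.0. The median odds ratio per SD of selected null variables, folded to lie above 1, was:

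| K | Stepwise | Univariate |
|---|---|---|
| 4 | 2.32 | 2.31 |
| 10 | 2.46 | 2.26 |
| 15 | 2.63 | 2.25 |

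Stepwise selection adds little at K = 4 and more as K grows. Across assumed failure rates of 10-30%, the median for the first variable selected lies at about 2 to 4 per SD, with the higher values at the lower rates. Per-unit odds ratios for binary candidates come out larger, because for an evenly split variable one unit is two SDs. They are not on the same scale.

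**The case against.** The SAP does not say that the regression is logistic, that it reports odds ratios, that entry is at 0.05, or that it looks for predictors. The sentence before it concerns an ordinal bother scale. The model might instead adjust the arm comparison, in which case the chance that some covariate reaches 0.05 is not the relevant error rate. The lack of a correction and of an exploratory label are both read from silence in a very short plan. Stepwise selection is also hardly worse than the univariate screen at entry 0.05, and the analysis serves no protocol objective.

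Most of this stands. The odds-ratio figures are conditional on a logistic model, every K above 4 is an assumption, and even K = 4 borrows a list made for another purpose. The main fault is multiplicity, with stepwise selection adding to it. What the objection does not remove is that the SAP gives these analyses the same significance rule as the primary test. For any screen of several variables, the table in Step 1 of the working then follows by arithmetic, whatever the outcome or model.

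A reader might infer that the trial's main result is compromised. The documents do not support that, because the primary outcome has its own unadjusted test that uses no selected covariates. A reader might also infer that invalid odds ratios will be reported. That goes too far, since neither document says that odds ratios are to be reported.

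**Conclusion.** The point holds in a conditional form and is minor. If several variables are screened, p-values of the selected ones do not hold at 0.05. The chance of at least one false finding is 18.5% for four independent null candidates and would reach 40.1% for ten or 53.7% for fifteen. Simulation at n = 60 gives similar or slightly higher rates for independent candidates. Exaggerated odds ratios, about 2 to 4 per SD for a variable with no effect, follow only if the model is logistic for voiding trial failure and failure rates are 10-30%. The consequence is confined to this secondary analysis. It is more than a missing detail, because the blanket p < 0.05 rule lets a chance selection be reported as significant and a reader could not tell how likely that is.

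**What to change.** Keep the unadjusted chi-square or Fisher comparison as primary. Replace stepwise selection with one small supportive model for failure of the first repeat voiding trial. Force the randomised arm in, and add at most one or two covariates fixed without reference to the outcome data, for example study center or one variable measured before randomisation. Under Design, "the subject will be called on POD#1 and randomized", so a variable that continues to accrue after that call, as post-operative narcotic use may, would need a cut-off before it. Penalised estimation is optional if failures are sparse.

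The SAP is written in the past tense, so the search may already have been run and disclosure may be the only remedy left. If the univariate or stepwise search is kept or already done, report its outcome, the full candidate list and the entry rule, label it exploratory, and do not apply the p < 0.05 significance rule to it.

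The cost is a few sentences in the SAP and report and one small model, with no new data. The downside is that fewer predictors can be explored and none can be claimed as significant.
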